#### **Washout period (1 - 4 weeks)**

There will be a one- to four week washout period between the control and intervention arms (or between intervention and control arms depending on randomization sequence). The use of the DailyDose app will be discontinued during this period for those participants who were randomized to start using DailyDose. Participants will use their own sensors during the washout period and will manage their glucose as they normally do. Participants are not required to weigh themselves, complete questionnaires, or wear the Apple Watch during this week. No visits are scheduled during the washout period.

#### **Study Completion session**

This visit will be completed within 2 weeks of completion of all study procedures. Participants will participate in a 1:1 online meeting with study staff. In this session, study staff will share with participants the factors that contributed to higher predicted probability of nocturnal low glucose during the study (e.g., if a certain type of exercise was to be the biggest contributor to nocturnal hypoglycemia risk). Participants will complete a short survey to evaluate usability aspects of the DailyDose overnight low glucose prevention module using a structured script. This meeting will take about 1 hour and will be recorded after receiving participant's authorization. Participants can also receive information about their risk factors for overnight low glucose and complete the closing survey over the phone in a call with study staff.

Participants will be given shipping boxes for sending all study devices back including the Apple iPhone, Apple Watch, Dexcom G6 transmitter and scale, as well as paper forms with weight records and survey responses. After this session all study devices will be turned in. If the 4-week DailyDose + smart snack intervention period or the control period are paused for a period of time

due to technical problems, the participant may be asked if they can complete additional time in study with the goal to collect at least 2 weeks worth of data in at least one of the arms of the study, such that the participant can be included in the statistical analysis. Additional compensation will be provided for additional time in study. Problems that would qualify for extending the study time are 1) insufficient study supplies requiring the participant to go off of DailyDose + smart snack intervention or to discontinue the control arm for a period of time (such as running out of CGM supplies or bedtime snacks), 2) issues with the smartphone such that DailyDose cannot be used/accessed (such as a due to a damaged phone or problems with the internet connection that prevent data from being uploaded to the remote monitoring system), 3) issues with the CGM system or the capture of the CGM data during the control period or during the intervention period such that DailyDose cannot generate bedtime recommendations due to insufficient CGM data, or 4) scheduling issues such that the participant is unable to complete the control or the DailyDose + smart snack intervention period continuosly. Participants can complete up to 4 additional weeks to make up time the study was paused for technical reasons. Repeating the study time will be optional. The study team will track when participants extend their study time and the reason and this will be included in the annual report to the FDA.

Table 3: Schedule of Events

 DailyDose abbreviated Dd

 Randomization order abbreviations Control first (CG) Intervention first (IG)

 (CG) only

(IG) only

Collect demographic and other baseline characteristics	X											
UPT if applicable and not done in last 7 days (Point of care)	X	X						X				
Collect blood sample for HbA1c, CBC, CMP, TSH testing	X											
Collect information about medical history	X											
Collect information about concomitant medications	X	X	X	X	X	X	X	X	X	X	X	
Download participant's glucose sensor	X											
Complete 3 surveys	X					X 					X 	
Randomization		X										
Collect data on Adverse Events		X	X	X	X	X	X	X	X	X	X	
Train participants on the study procedures to do at home		X					X					
Train participants on use of Dexcom G6 CGM system with G6 and Clarity apps		X 					X 					
Train participants on use of Apple Watch		X										
Collect sleep quality survey response			X	X	X	X		X	X	X	X	

## Stopping rule criteria

The study will be stopped if any of the following occur after the start of the study:

- The participant requests that the treatment be stopped
- Participant pregnancy
- One episode of diabetic ketoacidosis as defined as symptoms such as polyuria, polydipsia, nausea, or vomiting, serum ketones  $>1.5$  mmol/L or moderate/large urine ketones, either arterial blood pH  $<7.3$  or venous pH  $<7.24$  or serum bicarbonate  $<15$ , and treatment provided in a health care facility.
- One episode of severe hypoglycemia defined as a hypoglycemic event resulting in altered consciousness requiring another person to actively administer carbohydrate, glucagon, or other resuscitative actions.

## Cleaning and Disinfecting

All devices will be cleaned and disinfected between participants. The Apple iPhone and Apple Watch will be cleaned by study staff. Technicians who are disinfecting units will wash hands thoroughly and wear gloves. All items will undergo intermediate-level disinfection using Oxivir Tb Germicidal disposable wipes. The disinfectant will be applied and allowed to air dry. After disinfection, when the units are completely dry, they will be placed in a sealed bag labeled with subject information.

## Data Collection

We will be collecting de-identified physiologic data from people with T1D. The following data will be collected from participants in this study:

- Glucose sensor data (Dexcom G6 system)
- Self-report *bedtime snack* and exercise data logged by the participant on DailyDose
- Self-report weight logged by participant
- Sleep data from Apple Watch
- Responses to surveys

To collect the data, each participant in the study will be given an Apple iPhone and an Apple Watch. The iPhone will have the Dexcom G6 app and the DailyDose app installed. These apps will collect CGM data and log related to physical activity, bedtime snacks, and overnight low glucose predictions. The data from the Apple Watch will be exported from Apple Health or Apple iTunes as .cda or .xml files.

The DailyDose app will serve as the “data aggregator” on the phone and will perform the following functions:

- Collect self-report bedtime snacks and exercise data from the participants
- Aggregate all the data collected from the glucose sensor and self-logged snacks and exercise data
- to be stored as de-identified data within the iCloud storage area of the phone

### **DailyDose Guidance Remote Monitoring (GRM) Cloud Server**

All the data collected will be streamed over the Internet (using secure sockets encryption) to an OHSU secure instance of an AWS cloud storage server every five minutes. Authentication between the phone and the AWS server is done using self-expiring JSON Web Tokens (JWT). Data transmitted between the phone and the AWS server is encrypted using HTTPS/SSL. The code managing authentication and data transfer is Python version 3.7.0. Data acquired from the app is displayed via a physician web portal. The physician web portal user interface is written in Javascript version 1.8.5. There is no personally identifiable data stored with the data sent to the AWS server. The server shall be capable of receiving the following types of data from DailyDose (1) overnight low glucose predictions and smart snack recommendation data, (2) CGM data, (3) alerts, (4) settings. All types of data shall be indexed by subject ID and by date/time. Each data packet shall be accompanied by an authenticated JWT token. The AWS server has undergone a security review by OHSU IPS.

### **Confidentiality and Protection of Human Subjects**

Access to data/specimens is restricted to study personnel. Access to data requires OHSU ID/password authentication. See IRB protocol 19858 for a complete description of the confidentiality and security of the study data collected during this study to be stored in the OregonAPC repository. The data stored within the GRM Cloud Server and Dexcom Clarity is de-identified and does not contain any information from the 18 HIPAA designations of personally identifiable information. OHSU ITG has granted an Exception approval for using and storing data on the GRM. Data stored on the GRM will be deleted once the study is complete.

We will install the OHSU Intelligent Hub on the iPhones. Upon enrollment, participants will be assigned with a three-digit code to protect their privacy. The three-digit code will be used instead of their name, medical record number, or other personally identifying information. The key associating the code and the participants personal identifying information will be restricted to the PI and study staff. The key will be encrypted and kept secure on a restricted OHSU network drive in a limited access folder as stated below. The iPhones will be registered to the study participants' unique study ID number and all the data stored on the iPhone will be associated with this ID.

The three-digit identifying subject number will also be used to code paper study documents. Study staff will record data required by the protocol onto the Case Report Forms (CRF) during the study. The CRFs and all surveys will be collected on paper. Data for this project will be stored on the GRM, developed and maintained by our group, that has undergone a security review. Investigators and research coordinators will verify that the procedures are conducted according to the approved protocol. All paper source documents will be kept in a locked cabinet for a minimum of five years. The CRFs will include:

- Screening form
- Control arm start-up visit
- Control arm completion visit
- Intervention arm start-up visit
- Intervention arm completion visit
- Surveys

- Study completion visit
- Physician CGM Review Form
- Phone/Email Update Form
- Adverse Event form
- Serious Adverse Event form
- Concomitant Medications

The Principal Investigators may authorize other personnel to make entries in the CRF. The coded data will be stored in the OregonAPC repository according to IRB protocol 19858. The key to the code for this study will not be stored in the repository and only named study members on this project will have access to the key for this study. Researchers who request data from the repository will not receive any identifiers aside from date and we do not anticipate that the date will allow those researchers to re-identify the data. However, some of the researchers named on this project may use the data from the repository which would mean that the repository data will still be potentially identifiable to those who have access to the key as part of this project. During screening, all participants will sign the consent form to store their study data in the data repository.

To protect confidentiality, standard institutional practices will be followed to maintain the confidentiality and security of data collected in this study. Study staff will be trained with regard to these policies.

Paper files will be stored in locked filing cabinets in restricted access offices at site. After the study, source documents will be maintained at the participating clinical center (or offsite record storage facilities) 2 years after a marketing application is approved for our group's decision support device or discontinuance of pursuit of marketing approval. Electronic data will be stored on encrypted computers, laptops, and study smartphones. Electronic data is stored in OneDrive. DailyDose data will be housed in a custom cloud database on an OHSU secure server called the GRM. Access to data/specimens is restricted to study personnel. Access to data requires ID/password authentication.

## Risk and Benefits

**Risks:** The risks of the protocol procedures are considered minor. Daily management of glucose for people with type 1 diabetes brings a risk of hyperglycemia and hypoglycemia, but users are unlikely to experience severe low or high blood sugar because there are low and high glucose alerts available with the DailyDose app. Other risks are those associated with CGM use, but not directly related to this study. The following events have been identified as possible anticipated device-related adverse events of the FDA-approved Dexcom G6 sensor insertion and wear:

- Excessive pain or discomfort from either system deployment or during wear period (8 or greater on a 10-point Likert scale)
- Excessive bleeding, defined as requires removal of the device to stop bleeding
- Hematoma, defined as induration at the sensor insertion location (ecchymosis is a known consequence of needle skin puncture or pressure from sensor pod and will not be captured as an adverse events)
- Edema from sensor and/or adhesive tape that is significant and non-resolving within 48 hours of sensor pod removal

- Erythema from sensor and/or adhesive tape that is significant and non-resolving within 48 hours of sensor pod removal
- Local infection, defined as presence of pus at either sensor wire or sensor pod site
- Sensor or introducer needle fracture during insertion/wear/removal. For this reason, the study investigator will inspect each removed sensor for the possibility of breakage or fracture. Any evidence of sensor breakage will be recorded and reported to FDA and the sensor company.

There is a risk that the participant may consume a smart snack at night in response to the nocturnal low glucose alert and become hyperglycemic overnight. The DailyDose app will alert the participant if their glucose becomes too high using the high glucose alerts within the app. Participants will be instructed to manage high glucose levels as they usually do.

**Benefits:** The subject may not directly benefit from being in this study; however, their participation may help to advance decision support tools for preventing dangerously low glucose levels overnight.

## Costs

Participants will receive \$400 for completion of the study. If participants withdraw early from the study, compensation will be given as follows: \$40 per week for the control or DailyDose + *smart snack* periods. There is no compensation for the screening visit. If a participant completes additional time on study to make up for time the study was paused due to technical issues, participants will receive an additional \$40 per week.

## Monitoring Procedures

This investigation will be monitored by [name] and [name] [name]. [name] and [name] have no commercial interest in any of the companies which manufacture any of the devices used in this study. This protocol is written in accordance with the principles established by the 18th World Medical Assembly General Assembly (Helsinki, 1964) and amendments and clarifications adopted by the 29th (Tokyo, 1975), 35th (Venice, 1983), 41st (Hong Kong, 1989), 48th (Somerset West, South Africa, 1996), 52nd (Edinburgh, 2000), 53rd (Washington, 2002), 55th (Tokyo, 2004), 59th (Seoul, 2008), and 64th (Brazil, 2013) General Assemblies. The investigator will ensure that the study described in this protocol is conducted in full conformance with those principles, the protocol, current FDA regulations, ICH Good Clinical Practices (GCP) guidelines, Good Laboratory Practices (GLP) guidelines, local ethical and regulatory requirements, including the Federal Food, Drug and Cosmetic Act, U.S. applicable Code of Federal Regulations (title 21), any IEC requirements relative to clinical studies.

Should a conflict arise, the investigator will follow whichever law or guideline affords greater protection to the individual subject. The investigator will also ensure thorough familiarity with the appropriate use and potential risks of use of the study device, as described in this protocol, prior to the initiation of the study.

Unanticipated problems, including study, disease or device-related problems, will be detected by reviewing descriptions of known or foreseeable adverse events and risks in the IRB-approved research protocol and the current IRB approved consent form, any underlying disease or

conditions of the subject experiencing the adverse event, a careful assessment of whether the adverse event is related or possibly related to the subject's participation in the study or if root cause or associations is with study devices.

Triggers for reporting unanticipated problems are seizure, hospitalization, death, or any other occurrence considered serious by the PI. If ongoing monitoring of the studies reveals studies repeatedly being terminated because of unresponsive hyperglycemia or repeated serious hypoglycemia (resulting in altered mental status, loss of consciousness, or seizure), then the study will be discontinued immediately. If studies in two participants are stopped for severe hypoglycemia or severe hyperglycemia, then the entire study will be halted. Severe hypoglycemia is defined as an event requiring the assistance of another person to administer carbohydrate, glucagon, or resuscitative actions. Severe hyperglycemia is defined as capillary blood glucose that exceeds 300 mg/dl with serum ketones 3.0 mM or higher. In addition, if there is any unexpected event such as death or patient hospitalization, the studies will be stopped until the root cause is evaluated.

At all study visits, study staff will determine if any device, disease, or study-related adverse events (AEs) have occurred. Any adverse event (AE) and/or unanticipated problem (UP) will be reported to the investigator monitor immediately by one of the investigators. All study, disease or device-related AEs or UPs will be monitored until adequately resolved or stable.

Information regarding all AEs that occur during the study will be entered into appropriate CRFs. Such information will include, at a minimum:

- Date of event
- Severity
- Outcome
- Resolution of event

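### The participant stopping list and the two-participant halt define severe hypoglycemia and severe high glucose differently, so some severe events reach the halt count only by discretion.

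*Combined protocol and SAP*

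**What the plan says.** Two sections of the protocol govern stopping.

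Stopping rule criteria opens with "The study will be stopped if any of the following occur after the start of the study". Its first item is "The participant requests that the treatment be stopped", and its second is pregnancy. Two clinical events follow, each triggered by a single episode:
- **Ketoacidosis:** symptoms; serum ketones above 1.5 mmol/L or moderate to large urine ketones; low pH or serum bicarbonate below 15; "and treatment provided in a health care facility".
- **Severe hypoglycemia:** "a hypoglycemic event resulting in altered consciousness requiring another person to actively administer" carbohydrate, glucagon or other resuscitation.

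Monitoring Procedures sets the trial-level halt: "If studies in two participants are stopped for severe hypoglycemia or severe hyperglycemia, then the entire study will be halted". Its definitions come directly afterwards. For low glucose: "Severe hypoglycemia is defined as an event requiring the assistance of another person to administer carbohydrate, glucagon, or resuscitative actions". For high glucose: "capillary blood glucose that exceeds 300 mg/dl with serum ketones 3.0 mM or higher". The same section discontinues the trial on "studies repeatedly being terminated because of unresponsive hyperglycemia or repeated serious hypoglycemia (resulting in altered mental status, loss of consciousness, or seizure"), and pauses it for unexpected events, giving death and hospitalization as examples.

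Withdrawal Criteria lets the participant or the investigator end participation at will, but does not require it for these glucose events.

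**The concern.** The halt counts participants whose participation was stopped. Which participants must be stopped is set in another section with different event definitions, so an event can be severe under one and not the other. The threshold is only two, so a single participant left out of the count can decide whether the trial is halted.

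Assisted events are foreseeable here. The inclusion criteria admit people with previous severe hypoglycemia requiring third-party help and ask for a companion trained to give glucagon. What is at stake is participant safety and consistent application of the halt, not the primary efficacy analysis.

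**Working it through.** The protocol gives no operating characteristics for the halt, so there is no figure to reproduce. The check is a comparison of the two sections.

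**Step 1: level of the stopping list.** It speaks of the study being stopped, but a participant's request and a pregnancy can sensibly end only that person's participation. It is therefore read as a participant-level list.

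**Step 2: boundary cases.** Glucose is in mg/dL and serum ketones in mM. Ketoacidosis means that every criterion in the stopping list is met.

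| Event | Mandatory stop (Stopping rule criteria) | Severe (Monitoring Procedures) |
|---|---|---|
| Assisted hypoglycemia, altered consciousness | yes | yes |
| Assisted hypoglycemia, consciousness not altered | **no** | **yes** |
| Glucose 350, ketones 3.2, not treated in a facility | **no** | **yes** |
| Ketoacidosis, ketones 3.5, glucose 350 | yes | yes |
| Ketoacidosis, ketones 2.0, glucose 350 | **yes** | **no** |
| Ketoacidosis, ketones 3.5, glucose 280 | **yes** | **no** |
| Ketoacidosis shown by urine ketones only, glucose 350 | **yes** | **no** (no serum value) |

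Rows 2 and 3 are severe but have no mandatory stop. Rows 5 to 7 are stops that do not meet the definition attached to the halt.

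**Step 3: other rules that might close the gap.**
- *Withdrawal Criteria:* discretionary, so it can close the gap but need not.
- *Repeated-termination rule:* it also counts terminations, leaves open how many are needed, and limits hypoglycemia to altered mental status, loss of consciousness or seizure. It does not reach row 2. Its high-glucose limb has no numerical threshold and may catch rows 5 to 7.
- *Pause for unexpected events:* it may apply if a participant with ketoacidosis is admitted. Otherwise it turns on what counts as unexpected, and it adds nothing to the count of two.
- *Adverse event reporting:* row 3 has ketones above the 1.2 mM threshold, so it is recorded, and Monitoring Procedures sends adverse events to the investigator monitor at once. For row 2 the symptom list is open-ended but does not name third-party assistance. Recording is not the same as counting toward the halt.

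**Step 4: size, by assumption only.** Let p be the chance that a participant has an event that is severe under Monitoring Procedures, and g the share of such participants who are not stopped. Neither is in the documents. With independent participants and n = 20:

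P(halt) = 1 − (1 − q)^20 − 20q(1 − q)^19, where q = p if all are stopped and q = p(1 − g) otherwise.

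- p = 0.05, all stopped: 1 − 0.3585 − 0.3774 = 0.264.
- p = 0.05, g = 0.25, so q = 0.0375: 1 − 0.4656 − 0.3628 = 0.172.

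| p | g = 0 | g = 0.10 | g = 0.25 | g = 0.50 |
|---|---|---|---|---|
| 0.02 | 0.060 | 0.050 | 0.036 | 0.017 |
| 0.05 | 0.264 | 0.227 | 0.172 | 0.088 |
| 0.10 | 0.608 | 0.548 | 0.449 | 0.264 |

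These figures leave out ketoacidosis outside the Monitoring Procedures definition (rows 5 to 7). They show direction only and do not estimate the cost of the fix, which would add those stops to the count.

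**The case against.** The strongest reply is that the definitions in Monitoring Procedures immediately follow the halt sentence, so events meeting them are themselves grounds for stopping. On that reading rows 2 and 3 are counted. The reading is reasonable, and the stopping list does not claim to be exhaustive. But no sentence makes those events mandatory stops, and a safety rule should not depend on which reading staff adopt. What stands is that the definitions conflict; that events will in fact be missed is not shown.

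Other parts of the reply also stand. Row 2 may be rare: the Appendix B questionnaire links being unable to treat oneself with confusion, disorientation or lethargy, which an investigator might call altered consciousness. Risks and Benefits rates the procedures' risks as minor, and the intervention is a snack that participants may decline.

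A reader might be tempted by stronger conclusions that the documents do not support:
- *One episode ends the whole trial.* The opening words of the stopping list suggest this, but its participant-level items do not, and it would leave the two-participant rule largely redundant.
- *Severe events would go unseen.* Row 3 events are recorded and reported to the monitor, and row 2 events may be recorded.
- *The halt would be missed with a known probability.* No event or stopping rate is given, and if g is 0 nothing is missed.
- *The halt must count events instead of stops.* Once the definitions agree, counting stopped participants works.

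**Conclusion.** The conflict between the two sections is plain from the text and should be corrected, because it sits in a rule that decides whether the trial continues. It runs both ways: two kinds of severe event have no mandatory stop, and some ketoacidosis stops are not severe hyperglycemia for the halt, although the latter may be partly caught elsewhere. That uncounted events follow is conditional on the literal reading and on nobody using discretion to stop the participant. No size can be attached, since p and g in the illustration have no basis in the documents.

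**What to change.** Four wording changes:
1. In Stopping rule criteria, say that it is the participant who is stopped, not the study.
2. Use the assistance-based definition of severe hypoglycemia from Monitoring Procedures in both sections.
3. Add severe hyperglycemia, as Monitoring Procedures defines it, to the participant stopping list.
4. State that a ketoacidosis stop counts as severe hyperglycemia for the two-participant halt.

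The existing count of stopped participants can then stay. Counting qualifying events whether or not the participant was stopped is an option for the sponsor, useful if investigators are to keep judgement over individual stops. Naming third-party assistance among the examples in Adverse event reporting would also help.

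No visits or data are added. The cost is in conduct: participant stops and a trial halt may come somewhat more often in a trial of 20, or up to 23 with replacements. Some would arise from usual-care events in the control period, since participants are selected for recent overnight hypoglycemia. The sponsor should accept that trade-off knowingly; the documents do not allow it to be quantified.
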